### 7.3 DEFINITION OF AN UNEXPECTED ADVERSE EVENT

An **unexpected** adverse drug experience (event) is any AE, the specificity or severity of which is not consistent with information in the current IB for an unapproved IP or package insert/summary of product characteristics for an approved product (package inserts are available separately at the participating center).

### 7.4 DEFINITION OF SUSPECTED UNEXPECTED SERIOUS ADVERSE REACTION (SUSAR)

A SUSAR is a Suspected Unexpected Serious Adverse Reaction. An Adverse Reaction is defined as any AE caused by a drug. A suspected adverse reaction is defined as an AE for which there is reasonable possibility that the drug caused the AE. The "reasonable possibility" means that there is evidence to suggest a causal relationship between the drug and the AE. Any unexpected SAE that may be related to study drug is a SUSAR; however, unexpected SAEs that occur following treatment with a placebo solution usually does not qualify as a SUSAR. Because knowledge of treatment assignment during the main study is needed to complete the determination, the Sponsor's designee will provide the final determination as to whether an SAE is a SUSAR. During the LT-OLE the Sponsor will provide the final determination as to whether an SAE is a SUSAR.

### 7.5 NOTIFICATION ABOUT SERIOUS OR UNEXPECTED ADVERSE EVENTS

#### 7.5.1 Initial Notification

Each SAE must be reported by the Investigator to the Safety group immediately (within 24 hours) upon learning of its occurrence, even if it is not felt to be treatment-related. Follow-up information about a previously reported SAE must also be reported within 24 hours of the investigator receiving it. If the SAE is unexpected and is thought to be possibly related to the study drug, a Clinical Safety Associate shall urgently request further information from the investigator. This is essential for collecting information to report to the competent regulatory authority (RA).

- Any relevant reports (laboratory, discharge, etc.).

Accompanying documentation, such as copies of hospital case reports, autopsy reports and other documents when applicable, should be summarized on the SAE form and a copy of the source document may be sent if required. The patient's personal details will be removed and replaced with study identifiers i.e. study number and initials, if applicable.

In addition, all AEs / SAEs / SUSARs will be reported to the local Ethics Committees (EC) and RAs as required by local regulations and ICH-GCP guidelines.

Minimal information should include:

- An identifiable patient (e.g. patient study code number).
- An identifiable reporting source.
- All related AEs.
- The suspect medicinal product.

#### **Follow-Up of SAEs / SUSARs**

Follow-up of SAEs / SUSARs that occur during the study will continue until their satisfactory resolution or stabilization.

If supplementary information becomes available, a follow-up SAE Report Form must be completed by the site based on EDC system and emailed within 24 hours to Safety group.

The contact information for follow up SAE reporting is the same as for initial SAE reports (see above section).

The SAE form and accompanying documentation should be placed in the SAE section of the Investigator's file and/or patient medical file. If supplementary information on a SAE has to be sent, the SAE form to be used must be marked as "follow-up report".

#### **Follow-Up Reports on Non-Serious AE**

All AEs must be followed until resolution or stabilization. In exceptional cases, it may be defined as "ongoing without further follow-up" by the Investigator and Sponsor's decision.

### **7.6 REPORTING OF PREGNANCIES OCCURRING DURING THE STUDY**

Following administration of IP, pregnancy cases in any female patient (as well as in female partners of male patients) will be reported, if known, until the patient completes or withdraws from the study. The pregnancy will be reported immediately by phone and by faxing/emailing a completed Pregnancy Report to the Sponsor (or designee) within 24 hours of knowledge of the event. The pregnancy will not be processed as an SAE; however, the Investigator will follow the patient until completion of the pregnancy and must assess the outcome in the shortest possible time, but not more than, 30 days after completion of the pregnancy. The Investigator should notify the Sponsor (or designee) of the pregnancy outcome by submitting a follow-up Pregnancy Report. Dosing in the study should be stopped upon immediate notification of the pregnancy.

Effective Date: Date of final electronic approval

If the outcome of the pregnancy meets the criteria for immediate classification of an SAE (e.g., spontaneous or therapeutic abortion [any congenital anomaly detected in an aborted foetus is to be documented], stillbirth, neonatal death, or congenital anomaly), the Investigator will report the event by phone and by faxing/emailing a completed SAE Form to the Sponsor (or designee) within 24 hours of knowledge of the event, as outlined above.

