- Positive urine pregnancy test or confirmed pregnancy. In case of pregnancy, the study drug should be discontinued, and the Global Study MM be alerted immediately. All pregnancy tests used in this study, either urine or serum, must have a sensitivity of at least 25 mIU/mL and must be performed by a certified laboratory. Pregnancy tests will also be done whenever one menstrual cycle is missed during treatment (main study and LT-OLE) and when potential pregnancy is otherwise suspected and may be repeated if requested by institutional review boards (IRBs)/ethics committees (ECs) or if required by local regulations. In the case of a positive confirmed pregnancy, the patient will be withdrawn from administration of investigational product but may remain in the study for follow up.
- When the patient's annualized growth rate is  $\leq 2$  cm/12 months (the interval between two height measurements should be at least six months).

Patients can be re-screened for inclusion in the main study **one** time. Any data collected during the original screening period will be acceptable as historical data, EXCEPT safety laboratory data and IGF-1 and IGFBP-3 levels, which must be repeated and evaluated for eligibility. In this case, the patient will be assigned a new screening number.

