#### Male patients

The effect of MOD-4023 on sperm is not known.

The Investigator is obligated to discuss this issue of possible conception ahead of time with male patients and his parents/legal guardian. Patients are requested to refrain from sexual activity during the study i.e. observe complete sexual abstinence as the only acceptable contraceptive measure in this study.

If partner of the male patient becomes pregnant, the Investigator should be informed immediately. The patient doesn't need stop taking the study medication. The pregnancy will be reported to the Global Study MM, pharmacovigilance and Sponsor and follow-up period on mother and child will be defined based on individual basis and per discussion with DSMB.

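### Section 7.6 says to stop dosing on any reported pregnancy, a partner's included; Section 5.10 says a male patient whose partner is pregnant need not stop

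*Protocol*

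**What the plan says.** Protocol Section 7.6 (Reporting of Pregnancies Occurring During the Study) opens by setting its scope: "pregnancy cases in any female patient (as well as in female partners of male patients) will be reported". The same paragraph asks for a "completed Pregnancy Report to the Sponsor (or designee) within 24 hours of knowledge of the event", says that "the Investigator will follow the patient until completion of the pregnancy", and closes with a dosing instruction: "Dosing in the study should be stopped upon immediate notification of the pregnancy". Nothing in that closing sentence restricts it to one of the two kinds of pregnancy named at the start.

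Section 5.10 (Pubertal Assessment) treats the two kinds separately. A female patient who is, or thinks she may be, pregnant is asked to stop the study drug, and the reason given is possible harm to the fetus. Under the subheading Male patients, the section covers a pregnancy in the patient's partner and says: "The patient doesn't need stop taking the study medication". It continues: "The pregnancy will be reported to the Global Study MM, pharmacovigilance and Sponsor and follow-up period on mother and child will be defined".

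Section 4.4 lists reasons for discontinuation in the long-term open-label extension (LT-OLE). Under the item on the patient's own positive urine test or confirmed pregnancy it says: "In case of pregnancy, the study drug should be discontinued, and the Global Study MM be alerted immediately". It does not mention partners.

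The SAP supplied, which covers the LT-OLE, does not address the point.

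**The concern.** A dosing rule should give one answer for one event. Here a site that learns of a partner pregnancy can find two answers in current protocol text.

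The site has good reason to open Section 7.6. The Male patients text says whom to tell, but gives no form and no deadline; those are in Section 7.6. A coordinator who follows the reporting procedure therefore reaches the unqualified stop sentence, and nothing there points back to Section 5.10.

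What is at stake is an individual boy's treatment. Read literally, Section 7.6 would interrupt his growth hormone where Section 5.10 lets it continue. The statistical analysis is not at stake.

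**Working it through.** No arithmetic applies. The check is to set the instructions side by side by event.

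| Event | Section 4.4 (LT-OLE) | Section 5.10 | Section 7.6 |
|---|---|---|---|
| Pregnancy in a female patient | Stop | Stop | Stop |
| Pregnancy in a male patient's partner | Not mentioned | Need not stop | Stop, if read as written |

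1. **Does Section 7.6 reach partner pregnancies?** Yes. Its first sentence names them, and the rest of the paragraph speaks of the pregnancy without separating the two cases again.

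2. **Is the stop sentence limited in any other way?** Not expressly. The nearest thing to a limit is the follow-up wording, "the Investigator will follow the patient until completion of the pregnancy". This fits a patient who is herself pregnant and suggests that the author had her in mind. It does not undo the scope sentence, which includes partners.

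3. **Does Section 5.10 address the same event?** Yes. Its trigger is pregnancy in a male patient's partner, and its dosing instruction is the opposite of the literal one in Section 7.6.

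4. **Does either section reconcile the two?** No. The female-patient text of Section 5.10 refers to Section 7.6 for pharmacovigilance reporting. The male-patient text has no such reference, and Section 7.6 does not mention Section 5.10.

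5. **What was intended?** In Section 4.4 the stop follows the patient's own positive test or confirmed pregnancy. In Section 5.10 it follows her own suspected or confirmed pregnancy, for a reason that concerns the fetus of a patient taking the drug. The male-patient rule says outright that he may continue. All three point the same way: the stop is meant for the patient's own pregnancy.

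6. **Could the analysis be affected?** Children are pre-pubertal at entry and boys are under 12 at consent (Section 4.1), so a partner pregnancy is mainly a possibility for the LT-OLE. The SAP for that period plans no hypothesis test (Section 5.1) and includes data collected after treatment discontinuation (Sections 2.1.1 and 6.1.1). A stray interruption would change no test or conclusion.

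**The case against.** The strongest reply is that Section 5.10 already settles the matter. It has its own subheading for male patients, names this exact event and gives a dosing rule. Section 7.6 is about reporting, and its dosing sentence is general. A specific rule normally governs a general one, and the follow-up wording in Section 7.6 fits only a pregnant patient. In addition, a partner pregnancy is reported to the Global Study Medical Monitor, pharmacovigilance and the Sponsor under Section 5.10, with a 24-hour deadline to the Sponsor or its designee under Section 7.6, so a mistaken stop would probably be noticed.

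Most of this stands, and it is why the point ranks no higher. It shows the intent and limits the consequence. It does not remove the conflict: the protocol does not state that the specific section prevails, and Section 7.6 expressly brings partners within its scope.

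A reader might infer three stronger things, none of which the documents support:

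- **That Section 7.6 is a deliberate precaution for fathers.** Section 5.10 does say that the drug's effect on sperm is unknown. But the same subsection then says that the male patient need not stop, so the uncertainty was in view when the permissive rule was written.
- **That boys would lose treatment for long periods.** The reporting routes make a lasting wrongful stop unlikely, and no document describes one.
- **That the number or ages of boys at risk can be worked out from the LT-OLE bone-age and growth criteria.** They cannot. The documents give no rate of bone-age advance, and Section 4.4 lists these criteria as reasons for which participation may be ended, not as fixed exit points. No count of affected boys is given, and it may be zero.

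**Conclusion.** The inconsistency is real and both texts are current. For a pregnancy in a male patient's partner, Section 7.6 as written says to stop dosing and Section 5.10 says that stopping is not needed. For a pregnancy in a female patient, the sections agree.

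Severity is the lowest: a wording correction worth making because the stated rule, if followed, would needlessly interrupt a child's treatment. The event should be rare, given pre-pubertal entry and the abstinence agreement required for the LT-OLE (Section 4.1, criterion 13). No endpoint, estimate or conclusion changes.

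The finding of a conflict rests on reading the two instructions as written. The view that Section 5.10 holds the intended rule rests on Sections 4.4 and 5.10 taken together; the protocol nowhere says it in so many words.

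**What to change.** In Section 7.6, replace the dosing sentence with:

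> If a female patient becomes pregnant, her study drug should be stopped immediately upon notification of the pregnancy. For pregnancy in the partner of a male patient, study drug need not be stopped; see Section 5.10.

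This keeps the protection for a pregnant patient, agrees with Sections 4.4 and 5.10, and leaves the reporting duties for both kinds of pregnancy as they are. The cost is one replaced sentence, which can go into the next amendment or, before that, a letter to sites. Data collection and analysis do not change.

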### **7.7 INDEPENDENT DATA AND SAFETY MONITORING BOARD (DSMB)**

An independent and external DSMB will be established for the study, to periodically review the safety information generated during the conduct of the study and is allowed to request efficacy data if considered necessary for benefit/risk assessment. The primary responsibility of the DSMB is to provide guidance to the Sponsor regarding the safe conduct of the study based on their periodic review of safety data. The DSMB will review study safety summaries reported.

The DSMB's membership, full scope of responsibilities, operating procedures, data availability and reporting and record keeping requirements will be established by Sponsor and/or its representative. DSMB working procedures will be described in a DSMB Charter prior to enrolling the first patient.

The key safety data will be reviewed by an independent DSMB in approximately once every 4 months during the main study and approximately every 6 months during the LT-OLE. DSMB will also include review of number or percentage of patients requiring dose reductions due to IGF-1 > +2.0 SDS and number or percentage of patients whose IGF-1 remains above +2.0 SDS, despite dose reductions (in both MOD-4023 and Genotropin® cohorts). DSMB will also include review of number or percentage of patients requiring dose reductions due to AEs.

### **7.8 MEDICATION ERRORS**

Medication errors may result from the administration or consumption of the IP by the wrong patient, or at the wrong time, or at the wrong dosage strength.

Medication errors include:

- Medication errors involving patient exposure to the IP;
- Potential medication errors or uses outside of what is foreseen in the protocol that do or do not involve the participating patient.

Such medication errors occurring to a patient is to be captured in the EDC system.

### **7.9 MEDICAL DEVICE COMPLAINT REPORTING REQUIREMENTS**

All medical device complaints, regardless of whether the medical device complaint is associated with an AE, will be reported to the Sponsor on a designated form through a formal complaint system. Complaints may include incidents, potential incidents, and/or queries by clinical study patients and or clinical study site personnel on the function or use of the PEN or the drug product within the PEN. An incident or malfunction of the PEN is an event that might have led to death or serious deterioration in health, or if it occurred again might lead to death or serious deterioration in health.

Sponsor is to be notified of all medical device complaints within 24 hours of the Investigator's awareness of the event.

## 8. STATISTICAL ANALYSIS METHOD

### 8.1 SAMPLE SIZE CONSIDERATION

The aim of the main study is to demonstrate that weekly MOD-4023 is not inferior to daily r-hGH administration. Non-inferiority will be claimed if the 2-sided 95% CI for mean treatment difference (MOD-4023 – Genotropin®) in the primary efficacy endpoint will lie entirely above “non-inferiority margin” of -1.8 cm/year.

The following assumptions were made in the sample size calculation:

- 2-sided alpha of 0.05.
- 80 % power.
- Between-patient SD of annual growth rate is 2.5 cm/year in all treatment groups.
- Non-inferiority margin is -1.8 cm/year.
- The true mean treatment difference (MOD-4023 – Genotropin®) is -0.8 cm/year.

With these assumptions, 100 patients per group will provide 80 % power for the non-inferiority test. To allow for an approximate 10 % dropout rate, 110 patients will be randomized to each treatment group (Total N=220 patients).

### 8.2 ANALYZED POPULATION SETS

Five (5) analysis sets will be used for this study: Safety Analysis Set, Full Analysis Set, Full Analysis Subset (FAS), modified intent-to-treat (mITT) Set, and the per Protocol (PP) Set.

#### 8.2.1 Safety Analysis Set

The safety analysis set will include all patients who have received at least one dose of study treatment. Patients will be analyzed according to actual treatment received.

#### 8.2.2 Full Analysis Set

The full analysis set will include all patients randomized and will be the primary efficacy analysis set. Patients will be analyzed according to randomized treatment group.

If study enrollment is closed prior to subject full qualification and/or study closure for any other reason by the Sponsor and/or patients lost to follow up between Visit 1 and Visit 2, the patient will be excluded from the study.

#### 8.2.3 Modified Intent-to-Treat Set

The mITT set will include all patients who received at least one dose of study drug and had at least one post-baseline assessment of Ht. Patients will be analyzed according to randomized treatment group.

#### 8.2.4 Per Protocol Set

The PP set will consist of all randomized patients who did not have any major protocol deviations.

The patients who have any major protocol deviations will be identified before database lock by the clinical team in a blinded review.

### LT-OLE:

### 8.2.5 Full Analysis Subset

The term “full analysis subset” is used to describe the analysis set which is as complete as possible and as close as possible to the intention-to-treat (ITT) ideal of including all enrolled patients.

The full analysis set will comprise all treated patients who have received at least one dose of active treatment and who provide any follow-up data. The patients will be grouped by their original treatment in the treatment period.

### 8.3 HANDLING OF MISSING DATA

The method for handling missing data will be described in the SAP. The primary method of imputation will be with multiple imputation assuming missing at random, using SAS PROC MI. Details on all sensitivity analyses related to the handling of missing data will also be provided in the SAP.

#### LT-OLE:

No imputation will be made for missing measurements. Patients who discontinued early will have their last available data summarized.

### 8.4 ENDPOINTS

#### 8.4.1 Primary Efficacy Endpoint

The primary efficacy endpoint during the main study is the Annual HV in cm/year after 12 months of treatment.

*HV (cm/year) at Visit 8 (12 months)*

$$= (Ht \text{ at Visit } 8 - Ht \text{ at Visit } 2) / ((Date \text{ of Visit } 8 - Date \text{ of Visit } 2) / 365.25);$$

where Visit 2 is the Baseline visit.

(Note: HV at any other post-baseline *Visit xx* is also computed using formula above by replacing *Visit 8* with *Visit xx*).

#### 8.4.2 Secondary Efficacy Endpoints (Auxology/Clinical)

- Annualized HV after 6 months of treatment;
- Change in Ht SDS at 6 and 12 months, compared to Baseline;
- Change in bone maturation (BM) at the end of 12 months, compared to Screening bone age (BM calculated as BA/CA).

#### 8.4.3 Biochemical Endpoints

- Absolute IGF-1 and IGF-1 SDS levels on day 4(-1) after MOD-4023 dosing across study visits;
- IGFBP-3 and IGFBP-3 SDS levels at on day 4(-1) after MOD-4023 dosing across study visits.

#### 8.4.4 Safety Endpoints

- Incidence of AEs and SAEs;

Effective Date: Date of final electronic approval

- Incidence of anti-MOD-4023 Ab formation (including characterization of the Ab and neutralizing properties);
- Local injection site reaction assessment;
- Parameters of glucose metabolism: blood fasting glucose, fasting insulin level, HbA1c;
- Thyroid (endocrinology) status;
- Lipid profile;
- All other safety hematology, biochemical parameters and urinalysis;
- Physical examination;
- Fundoscopy results - if performed (normal/abnormal);
- Vital signs;
- ECG.

#### 8.4.5 Additional Endpoints

- Proportion of successful single injections out of total number of single injections using the MOD-4023 PEN in US patients at Wks 1, 2, 3, 4, 5, and 6, based on the PAT.
- Proportion of successful single injections out of total number of single injections using the MOD-4023 PEN in US patients at Wk 1, based on the OAT.
- Comments on the PAT related to successful or unsuccessful injection attempts.
- Comments on the OAT related to successful or unsuccessful injection attempts.
- Information gained by inspection of returned devices.
- QoL endpoint measured by the QoLISSY core questionnaire at Baseline and month 12 at specific countries per [Appendix L](#).

#### LT-OLE:

#### 8.4.6 Safety Endpoints

- Incidence of AEs and SAEs;
- Incidence of anti-MOD-4023 Ab formation (including characterization of the Ab and neutralizing properties);
- Local injection site reaction assessment;
- Parameters of glucose metabolism: blood fasting glucose, fasting insulin level, HbA1c;
- Thyroid (endocrinology) status;
- Lipid profile;
- All other safety hematology, biochemical parameters and urinalysis;
- Physical examination;
- Fundoscopy results - if performed (normal/abnormal);
- Vital signs;
- ECG.

#### 8.4.7 Auxology/Clinical Endpoints

- Annual HV in cm/year at each 12-month interval.

- Change in height SDS every 12 months (compared to the previous values).
- Change in bone maturation (BM) every 12 months, (compared to Week 52 BA (calculated as BA/CA) at completion of LT-OLE year 1 and to previous values from LT-OLE year 2 onwards).

#### 8.4.8 Biochemical Endpoints

- IGF-1 and IGF-1 SDS levels on day 4 (-1) after MOD-4023 dosing across study visits.
- IGFBP-3 levels and IGFBP-3 SDS on day 4 (-1) after MOD-4023 dosing across study visits.

